13.3 Reporting of adverse events

AEs reported by the subject or observed by the investigator must be recorded on the AE form of the eCRF and should be described in the following manner:

The *AE term* must be in precise English medical terminology (that is, not necessarily the exact words used by the subject). Whenever possible, a specific diagnosis should be stated (for example ‘allergic contact dermatitis’).

For cutaneous AEs, the *location* must be part of the AE description and may be described as [e.g. the face, scalp, back, chest, arm, leg, trunk or limb]. Additionally, the location should be described using the following terminology:

- Lesional/perilesional (≤ 2 cm from the border of lesion(s) treated with IMP).
- Distant (>2 cm from the lesion border).

The *duration* of the AE must be reported by the start date and stop date of the event (it will also be recorded if the event is ongoing). In addition, it will be recorded if the AE started prior to start of IMP.

AEs must be classified in terms of severity, causality and outcome according to the definitions in [Appendix 2](#).

Action taken with IMP: any action taken with IMP as a consequence of the AE must be recorded (dose not changed, drug withdrawn, not applicable, unknown).

Other action taken: any other action taken as a result of the AE must be recorded (none, concomitant medication, concurrent procedure).

Withdrawn from trial due to this AE: it must be recorded whether the AE led to withdrawal from the trial.

13.4 Reporting of serious adverse events

The criteria that define an AE as serious (that is, an SAE) are defined in [Appendix 1](#). SAE criteria are also listed on the SAE form.

13.4.1 Investigator reporting responsibilities

Any SAE must be reported to LEO on the (paper) SAE form within 24 hours of first knowledge. This report should contain an assessment of available information on seriousness, severity, causal relationship to the IMP, comparator or trial procedure, the action taken, the outcome to date, and a narrative description of the course of the event.

The completed SAE form must be faxed or scanned and e-mailed to Global Pharmacovigilance at LEO using the e-mail address or fax number below:

Global Pharmacovigilance at LEO

E-mail address: CCI [REDACTED]

Fax number: CCI [REDACTED]

If relevant, the investigator will enclose other information with the SAE form, such as anonymised reports of diagnostic procedures, hospital records, autopsy reports, etc.

Additionally, Global Pharmacovigilance at LEO may request further information in order to fully assess the SAE. The investigator must forward such information to LEO upon request by fax or e-mail (see contact details above).

The investigator must notify the local IRB(s)/IEC(s) of SAEs, as required by current applicable legislation for the concerned country.

SAEs occurring after the completion of the clinical trial should not be routinely sought or collected. However, such events should be reported to Global Pharmacovigilance at LEO (see contact details above) if the investigator becomes aware of them.

13.4.2 LEO reporting responsibilities

Global Pharmacovigilance at LEO is responsible for assessing whether or not an SAE is expected. The relevant reference safety information document for this clinical trial is:

For the IMP, the Investigator's Brochure for delgocitinib cream, edition 1 and subsequent updates must be used.

Global Pharmacovigilance at LEO will notify the regulatory authorities and concerned investigators of SAEs according to the current applicable legislation for the concerned country.

The IRB(s)/IEC(s) will be notified of SAEs according to the current applicable legislation for the concerned country.

For all non-US countries, the following reporting requirements apply: all SAEs which are assessed as causally related to the IMP(s) **by either the investigator or LEO** (ICH E2A Guideline), and which are unexpected (SUSARs), are subject to expedited reporting to regulatory authorities and IEC(s)/IRB(s) according to the current applicable legislation in the concerned country. Investigators will be notified of the evolving safety profile of the IMP on an ongoing basis.

For the US, the following reporting requirements apply: all SAEs which are assessed as causally related to the IMP(s) **by LEO** (Guidance for Industry and Investigators - Safety Reporting Requirements for INDs and BA/BE Studies; Guidance for Clinical Investigators, Sponsors, and IRBs: Adverse Event Reporting to IRBs – Improving Human Subject Protection) and which are unexpected (Serious and Unexpected Suspected Adverse Reactions [IND safety report]) are subject to expedited reporting to regulatory authorities and IRB(s). Investigators will be notified of the evolving safety profile of the IMP on an ongoing basis.

13.5 Other events that require expedited reporting

13.5.1 Pregnancy

Any pregnancy occurring during the clinical trial must be reported to LEO within 24 hours of first knowledge using the (paper) Pregnancy Form (Part I). All pregnancies must be followed up until delivery or termination and final outcome must be reported on the (paper) Pregnancy Form (Part II) within 24 hours of first knowledge.

The completed Pregnancy Forms must be faxed or scanned and e-mailed to Global Pharmacovigilance at LEO. Contact details are given in Section 13.4.1.

Pregnant subjects must immediately discontinue IMP permanently (Sections 10.2.1 and 10.3).

13.6 Reporting of other events

13.6.1 Adverse events of special interest

The event listed in Panel 13 is considered an AESI in this trial and will require that the investigator provides additional details to be recorded in the eCRF. An AESI may be serious (requiring expedited reporting, Section 13.4) or non-serious.

Panel 13: Adverse events of special interest

Adverse event of special interest	Additional information to be provided
Eczema herpeticum	Skin findings: 
 • Lesion type. • Disseminated/localized. • Location. • Present in area with visible eczema/no visible eczema/present in areas with and without eczema. • Monomorphic/polymorphic. Confirmation of herpes simplex virus.

13.6.2 Overdose

An overdose is defined as a subject using more than the recommended quantity of IMP specified in this protocol in Section 9.2 (at the investigator's discretion). An overdose is either accidental or intentional.

The term 'overdose' including a specification of why it occurred (accidental or intentional) must be documented on the AE form of the eCRF. In addition, AEs originating from overdose must be documented on a separate line. If the AE originating from the overdose qualifies as an SAE, expedited reporting is required (Section 13.4).

13.6.3 Medication error

Medication error refers to any unintentional error in the dispensing or administration of an IMP while in the control of the investigator or subject. Broadly, medication errors fall into 4 categories: wrong medication, wrong dose (including strength, form, concentration, amount), wrong route of administration, or wrong subject.

The medication error category must be documented on the AE form in the eCRF. In addition, AEs originating from a medication error must be documented on a separate line. If the AE originating from the medication error qualifies as an SAE, expedited reporting is required (Section 13.4).

13.6.4 Misuse

Misuse refers to situations where the IMP is intentionally and inappropriately used not in accordance with the protocol.

The term 'misuse' must be documented on the AE form in the eCRF. In addition, AEs originating from misuse must be documented on a separate line. If the AE originating from misuse qualifies as an SAE, expedited reporting is required (Section 13.4).

13.6.5 Abuse

Abuse relates to the sporadic or persistent, intentional excessive use of an IMP which is accompanied by harmful physical or psychological effects.

The term 'abuse' must be documented on the AE form in the eCRF. In addition, AEs originating from abuse must be documented on a separate line. If the AE originating from abuse qualifies as an SAE, expedited reporting is required (Section 13.4).

13.6.6 Aggravation of condition

Any clinically significant aggravation/exacerbation/worsening of any medical condition(s) (including the trial disease), compared to baseline, must be reported as an AE in accordance with Section 13.3 and 13.4.

13.7 Follow-up for final outcome of adverse events

During the trial, the investigator should follow up for final outcome on all AEs (including SAEs). Once a subject leaves the clinical trial, the investigator should follow up on the outcome of all non-serious AEs classified as of possibly/probably relationship to the IMP for 14 days or until the final outcome is determined, whichever comes first. SAEs must be followed up until a final outcome has been established, that is, the follow-up may continue beyond the end of the clinical trial. For SAEs which have stabilised and cannot be expected to recover during the trial or the safety follow-up periods, for example chronic or stabilised conditions, 'not recovered' is accepted as a final outcome and a statement that the SAE has stabilised or is chronic should be added to the narrative in the SAE form.

13.8 Handling of an urgent safety measure

An urgent safety measure is a measure taken to implement an action/protocol deviation under an emergency. This is defined as “...*the occurrence of any new event relating to the conduct of the trial or the development of the investigational medicinal product where that new event is likely to affect the safety of the subjects, the sponsor and the investigator shall take appropriate urgent safety measures to protect the subjects against any immediate hazard.*” (EU Directive 2001/20/EC).

If the investigator becomes aware of information that necessitates an immediate change in the clinical trial procedure or a temporary halt to the clinical trial in order to protect clinical trial subjects from any immediate hazard to their health and safety, the investigator can do so without prior approval from LEO, regulatory authorities, or IRBs/IECs.

The investigator must immediately inform LEO – by contacting the clinical project manager or medical expert – of this change in the clinical trial procedure or of the temporary halt providing full details of the information and the decision making process leading to the implementation of the urgent safety measure.

LEO must act immediately upon receipt of the urgent safety measure notification in accordance with internal procedures and local legislation.

14 Statistical methods

14.1 Sample size

A total of 250 subjects will be randomised 1:1:1:1:1 to one for the following 5 treatment groups: delgocitinib cream 1 mg/g, 3 mg/g, 8 mg/g, 20 mg/g or delgocitinib cream vehicle.

The sample size is based on the following pairwise consideration, even though the primary objective of the trial is to establish the dose-response relationship: With a significance level of 5% when comparing two treatment groups and assuming a difference in the mean change from baseline to Week 8 in EASI of 7 (with a standard deviation of 9 for each treatment group) between an investigational dose (delgocitinib cream) and delgocitinib vehicle, then 50 subjects per treatment group will provide a nominal power of at least 95% to detect a difference between two treatment groups. With 35–40 subjects per treatment group (e.g. in the subgroups of subjects with moderate or severe AD), there is approximately 90% power to detect a difference of 7 in mean change from baseline to Week 8 in EASI.

14.2 Trial analysis sets

All screened subjects will be accounted for in the CTR.

All randomised subjects exposed to IMP will be included in the full analysis set and will be analysed for efficacy parameters up to Week 8. Exclusions from the full analysis set can be considered in special cases as described in ICH E9, Section 5.2.1, Full Analysis Set. If it is decided to exclude a subject from the full analysis set, a justification addressing ICH E9 will be given.

A per protocol analysis set will be defined by excluding subjects from the full analysis set who fulfil any of the following criteria:

- Did not provide EASI or vIGA-AD data following start of treatment.
- Are known to have taken the wrong IMP throughout the treatment period of the trial.
- Did not fulfil the disease defining inclusion criteria (that is, inclusion criteria 3, 4, 5, and 6).
- Did not apply IMP at least 80% of the time in the period from date of first application of IMP to date of last application of IMP.

A safety analysis set will be defined as all randomised subjects exposed to IMP.

The decisions regarding inclusion/exclusion of subjects and/or subject data from the trial analysis sets will be documented in the analysis set definition document before breaking the randomisation code.

14.3 Statistical analysis

14.3.1 Disposition of subjects

The reasons for permanent discontinuation of IMP and withdrawal from trial will be presented for all randomised subjects by treatment group.

14.3.2 Demographics and other baseline characteristics

Descriptive statistics of demographics and other baseline characteristics will be presented for all randomised subjects by treatment group. Presentations of demographics, baseline disease severity, and proportion of subjects with baseline worst pruritus (“itch” – one of the symptoms captured in ADSD) (weekly average) above/below 4 on the NRS scale will also be given by region (North America (US and Canada) and Australia) and baseline disease severity (baseline vIGA-AD of 2, 3, and 4).

Demographics include age, sex, race, and ethnicity. Other baseline characteristics include vital signs, height, weight, body mass index, total IgE, Fitzpatrick skin classification, duration of AD, concurrent diagnoses (from medical history and indications for concomitant medication), concomitant medication, and previous AD treatments.

14.3.3 Exposure and treatment compliance

The duration of exposure to treatment in a specific visit interval will be calculated as the number of days from date of first application of IMP in that period to the date of last application of IMP in that period, both days included.

Exposure to treatment will be presented for the safety analysis set as days of exposure per treatment group.

Drug accountability data will be calculated by subtracting the weight of the used tubes from the mean normal weight of full tubes. Average weekly/bi-weekly and total usage will be presented per treatment group, respectively, both for time intervals between visits (1 or 2-week periods depending on the time between site visits) and total period.

Adherence to treatment regimen will be recorded in the eCRF. If any complications or deviations in administration are observed, these will be described as protocol deviations.

Adherence will be presented for the safety analysis set for each treatment group via the percentage of applications missed.

14.3.4 Testing strategy

This is a dose-ranging trial with the primary objective to establish the dose-response relationship. For the primary endpoint, change from baseline to Week 8 in EASI score, and the secondary endpoints, EASI75 at Week 8 and vIGA-AD TS, the selection of the dose-response model that fits data best will be controlled using a family-wise error rate of 5%. There will be no adjustment for the multiple testing of primary and secondary endpoints, all p-values will be considered nominal.

14.3.5 Analysis of primary efficacy endpoint

The primary endpoint, change from baseline to Week 8 in EASI, will be analysed for the full analysis set and for the per protocol analysis set. The per protocol analysis is regarded as supportive.

For the analysis of the change from baseline to Week 8 in EASI, data collected after permanent discontinuation of IMP or after initiation of rescue medication will not be included in the analysis. Missing data at Week 8 will be imputed using the MMRM predicted values from the below specified model for repeated measurements.

The MCP-Mod approach (see e.g. [EMA Qualification Opinion of MCP-Mod](#) or [Bretz et al. 2005](#) for further details of the framework) will be used to guide dose selection. The dose-response relationship for the continuous endpoint Change from baseline to Week 8 in EASI will be modelled by the following 3 identified candidate models. These candidate models are selected based on the expected dose-response.

Linear in log: $E_0 + \delta \times \log(d + c)$,

E_{max}: $E_0 + E_{\max} \times d / (ED_{50} + d)$,

Sigmoid E_{max}: $E_0 + E_{\max} \times d^h / (ED_{50}^h + d^h)$,

where d is the dose (incl. vehicle), E_0 is the efficacy offset (anticipated vehicle effect), E_{\max} is the asymptotic maximum effect, ED_{50} is the half-life value of E_{\max} , h is the steepness at ED_{50} , δ is the slope parameter, and c is a fixed offset parameter.

The models will be adjusted for the stratification variables region and disease severity (baseline vIGA-AD of 2, 3, and 4). The model parameters (ED_{50} , h) will be prespecified a priori by suitable guesses based on data from Japan Tobacco's dose-ranging trial QBA2-1 (Nakagawa et al. 2018). Akaike's Information Criteria will be used as the goodness-of-fit criterion that will drive the selection of the dose-response model that fits data best while controlling the family-wise error rate at 5%. Based on the selected model, the dose-response relationship will be estimated and presented with 2-sided 95% CI. If none of the candidate models converge, other possibilities of models and goodness-of-fit criteria will be explored. The dose-response modelling will be performed on both the total population and subjects having a baseline vIGA-AD of 3 or 4, in order to further explore heterogeneity in the disease population.

In addition to the dose-response modelling approach, the continuous endpoint will be analysed using an MMRM on the post baseline responses up to Week 8 with an unstructured covariance matrix, Kenward-Roger approximation to estimate denominator degrees of freedom, and the mean modelled as follows:

Change from baseline in EASI

$$= \text{treatment} \times \text{visit} + \text{baseline EASI} \times \text{visit} + \text{region} + \text{baseline vIGA-AD}$$

The estimates will be presented with nominal p-values and 95% CI at each visit. The primary comparison between each delgocitinib dose and vehicle will be at Week 8.

Sensitivity analysis will be performed as applicable in order to assess the robustness of results of the primary analysis with respect to the retrieved data at Week 8 and assumptions regarding missing data. This will be described in further detail in the statistical analysis plan.

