9.5 Rescue treatment

If medically necessary (i.e. to control intolerable AD symptoms), rescue medication for AD may be provided to trial subjects at the discretion of the investigator. The investigators should make every attempt to conduct efficacy and safety assessments (for example disease severity scores, safety laboratory assessments) immediately before administering any rescue treatment.

If rescue medication is initiated, the subject must stop treatment with IMP immediately and must not restart treatment with IMP. It must be stated in the eCRF that the subject receives rescue medication.

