10.3 Early termination assessments

An end of trial form must be completed for all subjects, including subjects who withdraw from the trial or discontinue IMP treatment, at their last trial visit (the early termination visit, the safety follow-up visit, or the primary endpoint visit, whichever comes last).

Withdrawal from trial

Subjects who withdraw from the trial must attend an early termination visit as soon as possible after last administration of IMP (see the schedule of trial procedures [Section 4] for data to be collected at an early termination visit). The investigator will review any AEs which will be followed-up according to Section 13.7, if the subject agrees.

Discontinuation of IMP

Subjects who discontinue IMP for any reason prior to Week 8 will be asked to attend an early termination visit as soon as possible after last application of IMP and return to the trial site for 2 additional visits as indicated below. See the schedule of trial procedures (Section 4) for data to be collected at these visits.

Subjects who discontinue IMP prior to Week 8 will be asked to attend:

- Early termination visit (as soon as possible after the last IMP application).
- Safety follow-up visit (2 weeks after last application of IMP).
- Primary endpoint visit (8 weeks after the first IMP application).

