14.3.12 General principles

Unless otherwise stated, all significance tests will be 2-sided using the 5% significance level. All CIs will be presented with 95% degree of confidence.

An observed-cases approach will be used for tabulations of data by visit (i.e. involving only those subjects who attended each specific visit).

Categorical data will be summarised using the number and percentage of subjects in each category and treatment group. Continuous data will be summarised using the mean, median, standard deviation, minimum, and maximum values.

All the analyses specified in the protocol will be reviewed in relation to the blinded data actually obtained and the statistical analysis plan will be finalised before breaking the randomisation code.

Any changes from the statistical analysis planned in this clinical trial protocol will be described and justified in a protocol amendment, the statistical analysis plan and/or in the CTR dependent on the type of deviation.

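### Read literally, the primary analysis drops the EASI from the early termination visit, and a pre-rescue EASI between scheduled visits has no schedule entry or visit assignment, so predicted Week 8 values can be too favourable.

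*Combined protocol and SAP*

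**What the plan says.** **Analysis rule.** Section 14.3.5 states that, for change in EASI to Week 8, "data collected after permanent discontinuation of IMP or after initiation of rescue medication will not be included in the analysis". Missing Week 8 values are replaced by MMRM predictions. MCP-Mod is then fitted, and the MMRM is also reported as an additional analysis.

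**Early termination.** Section 10.3 lists, for subjects who stop IMP before Week 8, "Early termination visit (as soon as possible after the last IMP application"). Footnote d of Panel 2 gives this visit every Week 8 procedure except the biopsy, so EASI is scored. Panel 2 puts early termination and Week 8 in one column.

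**Rescue.** Section 9.5 asks investigators to try to obtain efficacy assessments, disease severity scores among them, "immediately before administering any rescue treatment". Starting rescue ends IMP for good.

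**Unscheduled visits.** Footnote g of Panel 2 allows them for, among other reasons, a marked change in disease state. That column has entries for vital signs, ECG, laboratory tests, adverse events and new lesions, but none for EASI or vIGA-AD.

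**Visit assignment.** The MMRM in Section 14.3.5 has treatment-by-visit terms at the scheduled visits. It has no rule for placing an early termination or unscheduled value. Sensitivity analyses on retrieved Week 8 data and missing-data assumptions are promised, with details left to the statistical analysis plan.

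**The concern.** MMRM prediction is valid if, given the observed values, stopping does not depend on values the model lacks. The EASI scored when the subject stops is often the value that explains the stop. If it is removed, or never recorded, Week 8 is predicted from earlier visits as though the worsening had not occurred.

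This can happen in two ways, which need separate remedies:

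- **Early termination value:** collected, but excluded on a literal reading.
- **Pre-rescue value between visits:** asked for and not excluded, but with no schedule entry and no place in the model.

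In each arm the predicted Week 8 mean then shows too much improvement. If vehicle has more such stops, its mean is distorted more, the vehicle level (E0) in the dose-response curve is shifted, and the estimated drug effect shrinks.

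**Working it through.** **1. The plan's own power figure.** Inputs from Section 14.1: significance level 5%; "assuming a difference in the mean change from baseline to Week 8 in EASI of 7"; SD 9 in both arms; 50 per group. Section 14.3.12 makes tests two-sided.

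- SE of a difference = 9 × √(2/50) = 1.8.
- Power = Φ(7/1.8 − 1.960) = Φ(1.929) = 97.3% (97.1% with the noncentral t).
- This agrees with the claim that "50 subjects per treatment group will provide a nominal power of at least 95% to detect a difference between two treatment groups". With 35 per group the normal formula gives 90.2%, and with 40 it gives 93.6%.

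**2. The texts side by side.**

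| EASI value | Excluded by Section 14.3.5? | Entry in Panel 2? | Visit assignment stated? |
|---|---|---|---|
| Scheduled Week 1, 2, 4 or 6 visit at which the stop or rescue is decided | No | Yes | Yes |
| Completer's Week 8 visit, after the last application at home (Sections 7.1 and 9.2) | No | Yes | Yes |
| Early termination visit, days after the last application, before rescue | Yes, read literally | Yes, in the Week 8 column | No |
| Just before rescue, at an unscheduled visit | No | No | No |

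The second and third rows differ little in time since the last application, so that interval alone does not explain the different treatment.

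**3. Size.** The documents give no stopping rate, rescue rate or correlation between visits. Everything below rests on assumptions. Negative change is improvement. Bias in the difference = bias(active) − bias(vehicle); a positive value brings −7 closer to zero. Power = Φ((7 − bias)/1.8 − 1.960), with SD held at 9.

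*Simulation A.* 60,000 per arm. Mean change runs over the visits from −2 to −5 on vehicle and −4 to −12 on active. SD rises from 6 to 9, with AR(1) correlation 0.8. The probability of stopping is logistic in the current EASI change, and the value at stopping is dropped.

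| Stopping, vehicle/active | Bias, vehicle/active | Bias in difference | Power |
|---|---|---|---|
| 6%/5% | −0.10/−0.07 | 0.03 | 97.2% |
| 13%/8% | −0.27/−0.16 | 0.11 | 96.9% |
| 23%/14% | −0.58/−0.36 | 0.22 | 96.5% |
| 31%/20% | −0.80/−0.54 | 0.26 | 96.3% |

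With the value at stopping kept, bias was within 0.05.

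*Simulation B.* 200,000 per arm. Week 8 mean change is −3 on vehicle and −10 on active. SD rises from 6 to 9, with equal correlation 0.5 or 0.7 between visits. A subject stops at the first value above a threshold, and that value is always lost.

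| Stopping, vehicle/active | Bias, vehicle | Bias, active | Bias in difference | Power |
|---|---|---|---|---|
| 10%/2% | −0.74 to −0.80 | −0.19 to −0.20 | 0.53 to 0.61 | 94–95% |
| 20%/6% | −1.58 | −0.49 to −0.57 | 1.01 to 1.08 | 91% |
| 30%/10–11% | −2.35 to −2.50 | −0.86 to −1.07 | 1.43 to 1.49 | 86–87% |

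If half the flare values are seen, the bias in the difference halves, to 0.26–0.30, 0.49–0.54 and 0.71–0.73. If all are kept, it is at most 0.02.

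Both simulations drop a value that belongs to a scheduled visit, which the plan would normally keep. Simulation B also lets the Week 8 value itself trigger a stop and be lost. They show direction and order of size under a worst case, with two arms; Simulation B has no baseline covariates.

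**The case against.** **Permanent discontinuation is not the same as the last application.** Completers' Week 8 EASI also follows the last application, so a prompt early termination value could be read as included. This stands as far as it goes: exclusion is the literal reading, not the only one. An analyst still has to choose, and the text does not settle it.

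**Some slots exist.** A subject who needs rescue should attend early termination, where EASI is scored, and a pre-rescue score can be recorded there if the visits coincide. That is true, but that value then meets the exclusion rule and has no visit assignment.

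**The effect may be small.** In Simulation A at 13%/8% and 31%/20% stopping, the bias in the difference is 0.11/1.8 = 6% and 0.26/1.8 = 14% of one standard error, and power stays above 95%. This stands. The several-fold gap between the simulations shows that the size is unknown.

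**Other analyses help.** Week 8 EASI is sought from subjects who stop, sensitivity analyses are promised, and Section 14.3.6 counts rescued subjects as non-responders for the binary endpoints. These are real safeguards. However, Section 14.3.5 does not mention early termination values, and no sensitivity analysis recovers an EASI that was never recorded. The separate analysis plan to which details are deferred is not in the text reviewed, so a windowing rule there cannot be ruled out.

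**Stronger readings that a reader might infer, and that the documents do not support:**

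- *The plan discards the pre-rescue EASI.* It precedes both rescue and the stop that rescue triggers, so the exclusion does not reach it.
- *The model never sees the flare.* A flare acted on at a scheduled visit is on-treatment, before rescue and in the model.
- *The drug effect is overstated.* Improvement is over-predicted within each arm, but the difference shrinks if vehicle stops dominate. It would grow only if such stops were commoner on active treatment.

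**Conclusion.** The point holds as a gap in definition and scheduling. Read literally, the plan removes the early termination EASI, and it neither schedules nor places a pre-rescue EASI taken between visits. Where stopping is driven by worsening between scheduled visits, the MMRM-predicted Week 8 values that enter MCP-Mod can be too favourable.

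The size cannot be derived from the documents. Under assumed stopping the loss in the difference is about 0.1 to 0.3 EASI points (Simulation A, 13% or more stopping on vehicle) or 0.5 to 1.5 points (Simulation B, sharper rule, flare value always lost), against a planned difference of 7 and a standard error of 1.8. Both ranges assume more stops on vehicle. At about 6% stopping in Simulation A, the effect on the difference is negligible (0.03). The change is worth making because it is cheap and because keeping the value at stopping removed nearly all the bias in both simulations.

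**What to change.** 1. In Section 14.3.5, count an EASI as on-treatment if it precedes any rescue and is taken within a stated window of the last application, for example 3 days, including at early termination.
2. Assign it to the nearest scheduled post-baseline visit. Ties (Days 22, 36 and 50) go to the later visit. If two values fall on one visit, use the latest eligible one. Use a value as Week 8 only if it falls within Day 57 ±3 (Days 54 to 60). Days 50 to 53 are then nearest to Week 8, or tied to it, but barred from it, so state where those values go; Week 6 is the simple choice.
3. Mark EASI and vIGA-AD as conditional, (X), in the unscheduled column of Panel 2, so that it agrees with Section 9.5.
4. Repeat the primary analysis without these values as a sensitivity analysis.

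The cost is some analysis wording and a conditional schedule and eCRF entry for scores that Section 9.5 already requests. The downside is that a few values up to 3 days off IMP enter the model; item 4 shows their influence. No rescue or stopping rule changes.
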